4.9 Handling of missing or partial dates

For patients not known to have died prior to the analysis cut-off date:

- All events with start date before or on the cut-off date, and with end date missing or after the cut-off date or after the date of withdrawal of informed consent will be reported as 'Continuing'.
- This approach applies, in particular, to AEs and concomitant medication reports. For these events, the end date will not be imputed and therefore will not appear in the listings.

If imputation of an end date is required for a specific analysis (e.g., for a dose administration record with missing end date or last date of study drug after the cut-off date), the end date will be imputed to the min (analysis cut-off date, death date, withdrawal of informed consent date) for the purpose of calculating duration of exposure to study drug and dose intensity. The imputed date will be displayed and flagged in the listings.

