2.6 Treatments (study drug, concomitant therapies, compliance)

The Safety Set will be used for all medication data summaries and listings unless otherwise specified.

Study drug and study treatment

Study drug and study treatment both refer to LDK378 and will be used interchangeably.

Date of first/last administration of study drug

The date of first administration of study drug is defined as the first date when a non-zero dose of study drug was administered and recorded on the [Dosage Administration Record (DAR)] eCRF page. For the sake of simplicity, the date of first administration of study drug will also be referred to as start date of study drug.

The date of last administration of study drug is defined as the last date when a non-zero dose of study drug was administered and recorded on the DAR eCRF page. This date will also be referred to as last date of study drug.

Study day

The study day for all assessments (e.g., tumor assessment, death, disease progression, tumor response, performance status, adverse event onset, laboratory abnormality occurrence, vital sign measurement, and dose interruption) will be calculated using the start date of study drug as the origin. For assessments occurring after or on the start date of study drug, study day will be calculated as:

Study day = Event date – Start date of study drug + 1.

The first day of study drug is therefore study day 1.

For any assessment or events such as baseline disease characteristics or medical history (e.g., time since diagnosis of disease) occurring prior to the start of the study drug, study day will be negative and will be calculated as:

Study day = Event date – Start date of study drug.

The study day will be displayed in the relevant data listings.

Dose exposure and intensity

Definitions of study drug exposure variables, as well as intermediate calculations, are provided in [Table 2-1](#).

Table 2-1 Study drug exposure variables

Variable	Definition
Duration of exposure (days):	Last date of study drug – Start date of study drug + 1 (Periods of interruption are not excluded.)
Cumulative dose (mg):	Total dose of study drug taken by a patient in the study
Number of dosing days (days):	Duration of exposure (days) – Number of zero dose days
% of actual days dosed (%):	$100 \times \text{Number of dosing days} / \text{Duration of exposure (days)}$
% of days received full dose (%):	$100 \times \text{Number of days received full (planned) dose} / \text{Duration of exposure (days)}$

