2.8.2 Safety

All safety analyses will be performed based on the Safety Set. All listings and tables will be presented for all patients, unless otherwise specified.

Baseline

Baseline is the result of an investigation describing the “true” uninfluenced state of the patient. The last available assessment before or on the start date of study drug is defined as “baseline” value or “baseline” assessment. If an assessment is planned to be performed prior to the first dose of study drug in the protocol and the assessment is performed on the same day as the first administration of study drug, it will be assumed that it was performed prior to study drug administration, if assessment time or first dose time is not collected or is missing. If assessment time and first dose time are collected, the observed time point will be used to determine pre-dose on study day 1 for baseline calculation. Unscheduled assessments before the start date of study drug will be used in the determination of baseline. See [Section 4.8.2](#) for further details on derivation of baseline for laboratory data and ECGs.

Patients who start study treatment and discontinue from the study on the same day may have 2 different sets of data collected on study day 1, one being reported to the cycle 1 day 1 visit, the other reported to the end of treatment (EOT) visit. Data reported at the EOT visit are not eligible for baseline selection.

Grouping for the analyses

The overall observation period will be divided into three mutually exclusive segments:

- Pre-treatment period: from day of patient’s informed consent to the day before first dose of study drug.
- On-treatment period: from day of first dose of study drug to 30 days after last dose of study drug (Note: for ongoing patients, from day of first dose of study drug to the data cut-off date).
- Post-treatment period: starting at day 31 after last dose of study drug.

The safety summary tables will include only assessments collected during the on-treatment period, i.e., assessments collected no later than 30 days after last dose of study drug and assessments collected before or on the data cut-off date for ongoing patients, unless otherwise specified.

For select items, shift tables or change from baseline summaries generated for laboratory, ECG, vital signs and change score generation may use data from pre-treatment period for baseline calculations.

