4.9.7 Incomplete date for last dose of study drug

Scenario 1

If the last date of study drug is after the analysis cut-off date or is completely missing and there is no [End of Treatment Phase Disposition] eCRF page and no death date, the patient should be considered to be on-going and use the cut-off date for the analysis as the last dosing date.

Scenario 2

If the last date of study drug is completely or partially missing and there is EITHER an [End of Treatment Phase Disposition] eCRF page OR a death date available then imputed last dose date:

= 31DECYYYY, if only Year is available and Year < Year of min (EOT visit date, death date).

= Last day of the month, if both Year and Month are available and Year = Year of min (EOT visit date, death date) and Month < the month of min (EOT visit date, death date)

= min (EOT visit date, death date), for all other cases

The imputed date will be compared with start date of study drug. If the imputed date < start date of study drug, then last date of study drug is set to start date of study drug; otherwise, use the imputed date.

5 Reference:

Brookmeyer R and Crowley J (1982). A Confidence Interval for the Median Survival Time, *Biometrics* 38, 29 - 41.

Clopper CJ and Pearson ES (1934). The use of confidence or fiducial limits illustrated in the case of the binomial. *Biometrika*; 26, 404-413.

Collet D (1994). Modelling survival data in medical research. London, Chapman & Hall.

FDA (2007). Guidance for Industry Clinical Trial Endpoints for the Approval of Cancer Drugs and Biologics, US Department of Health and Human Services.

Kalbfleisch JD and Prentice RL (2002). The Statistical Analysis of Failure Time Data. Wiley Series in Probability and Statistics.

Klein JP and Moeschberger ML (1997). Survival analysis: Techniques for censored and truncated data. New York, Springer.

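### SAP 4.9 and SAP 4.9.7 give different last-dose dates for the same patient, and neither says which governs

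*SAP*

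**What the plan says.** SAP 2.6 takes the last date of study drug from the dosage administration record: the last day with a non-zero dose. Table 2-1 then defines duration of exposure as "Last date of study drug – Start date of study drug + 1", and dose intensity and relative dose intensity (RDI) are built on that duration.

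Two sections supply this date when it is missing.

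- **SAP 4.9** applies where an end date is needed for a specific analysis. Its examples are "for a dose administration record with missing end date or last date of study drug after the cut-off date". The rule is that "the end date will be imputed to the min (analysis cut-off date, death date, withdrawal of informed consent date", and it is used "for the purpose of calculating duration of exposure to study drug and dose intensity".
- **SAP 4.9.7** deals with the last dose of study drug by name. Scenario 1 is for a patient with neither an EOT page nor a recorded death, and its instruction reads: "the patient should be considered to be on-going and use the cut-off date for the analysis as the last dosing date". Scenario 2 is for a wholly or partly unknown date, on the condition that "there is EITHER an [End of Treatment Phase Disposition] eCRF page OR a death date available then imputed last dose date". It gives a year end or month end for some partial dates, and otherwise "min (EOT visit date, death date), for all other cases".

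Neither section refers to the other.

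**The concern.** Both rules feed the same variable, but their lists of candidate dates differ. SAP 4.9 has consent withdrawal and no EOT date. SAP 4.9.7 has the EOT date and no consent withdrawal. Two programmers could each follow the SAP faithfully and produce different exposure tables.

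Neither rule is right throughout. A completed EOT page shows that dosing has stopped, and Protocol 4.1.2.2 and 7.1.3 place the EOT visit within 7 days of the last dose. Running such a patient's exposure to the cut-off is therefore wrong. Conversely, Protocol 7.1.4 requires study treatment to stop when consent is withdrawn, so calling that patient ongoing is also wrong.

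At stake are duration of exposure, cumulative dose, dose intensity and RDI, in a study small enough for one misdated record to show in a mean, a range or a category count.

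**Working it through.** The plan gives no figure of its own on this point, so there is nothing to reproduce. The check applies both rules as written to the same hypothetical patients.

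**Inputs**
- Rule A (SAP 4.9): min(cut-off, death, consent withdrawal).
- Rule B (SAP 4.9.7): the cut-off if there is neither an EOT page nor a death date; otherwise min(EOT visit, death).
- Duration = last date − start date + 1 (SAP Table 2-1). With first dose on day 1, duration equals the study day of the last dose.
- Cut-off: SAP 2.1 puts the primary cut-off about 168 days after the last patient's first dose. Day 168 is therefore roughly the shortest case, and later cut-offs are assumed.
- EOT, death and withdrawal days are assumptions; the documents give none.

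**Step 1: the two rules side by side** (last-dose date completely missing, cut-off day 168)

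| Patient | Rule A (days) | Rule B (days) |
|---|---|---|
| EOT day 56, alive, consent kept | 168 | 56 |
| EOT day 56, died day 120 | 120 | 56 |
| Consent withdrawn day 50, no EOT page, no death date | 50 | 168 |
| Ongoing | 168 | 168 |
| Died day 60, no EOT page | 60 | 60 |
| Consent withdrawn day 50, EOT day 50 | 50 | 50 |

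The rules agree in the last three rows and disagree in the first three. In the first row the 4.9 date is too late; in the third the 4.9.7 date is.

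**Step 2: effect on mean exposure**, for one affected patient of the first kind among 20
- EOT day 56, cut-off day 168: (168 − 56)/20 = 112/20 = 5.6 days.
- EOT day 60, cut-off day 500: (500 − 60)/20 = 440/20 = 22 days.
- With cut-off day 168, moving EOT from day 28 to day 140 takes the shift from 140/20 = 7.0 to 28/20 = 1.4 days. With cut-off day 365 it goes from 337/20 = 16.85 to 225/20 = 11.25 days.

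**Step 3: effect on dose measures**, taking 750 mg/day up to EOT. The result under 4.9 depends on how the open record is handled.
- Dose counted only to EOT:
  - EOT day 56, cut-off day 168: 56 × 750 = 42,000 mg; 42,000/168 = 250 mg/day; RDI = 250/750 = 33.3% instead of 100%.
  - EOT day 60, cut-off day 500: 60 × 750 = 45,000 mg; 45,000/500 = 90 mg/day; RDI = 90/750 = 12% instead of 100%.
- Open record counted as dosed to the cut-off: RDI stays at 100% and cumulative dose is inflated instead, to 168 × 750 = 126,000 mg against 42,000 mg, or 500 × 750 = 375,000 mg against 45,000 mg.

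Duration is wrong either way. What changes is which of the other two measures is wrong with it.

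**The case against.** The best defence is that a specific rule displaces a general one. SAP 4.9 opens the date-handling section, its imputation sentence is conditional, and 4.9.7 is a dedicated algorithm that expressly covers a patient with an EOT page. A sensible programmer would use 4.9.7 there. This has force for the first situation, although the SAP does not say so and 4.9 names dose records and exposure outright. It does not help with the second, where 4.9.7 is the rule that goes wrong.

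The second situation also needs two data failures. Protocol 7.1.3 requires an EOT disposition page on discontinuation, and Protocol 9.4 sends missing values back to the site as queries. That stands: the case should be rare.

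A reader might also infer that the 4.9 date stretches the safety window, defined as "from day of first dose of study drug to 30 days after last dose of study drug", and so changes which adverse events, laboratory values and ECGs are tabulated. The text does not support this. In the first situation, 4.9 confines itself to exposure and dose intensity, so the window would take its date from 4.9.7. In the second, the 4.9.7 date would lengthen the window, but SAP 2.1 bars reporting of data collected after consent is withdrawn, so little or nothing would enter. What does remain is that one patient could carry two last-dose dates in the same report.

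Nor should the 12% RDI be read as the outcome to expect. It needs a long assumed gap and a cumulative dose that is not extended with the open record.

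**Conclusion.** The conflict is real. Its consequence is limited to descriptive exposure and dose-intensity summaries. Choosing either section as it stands leaves one kind of patient misdated, so a statement of precedence alone is not enough.

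The size rests on assumed dates and on an unknown number of affected records, probably few of about 20. One patient with an EOT page moves mean exposure by 5.6 to 22 days in the two main examples, with either RDI or cumulative dose distorted as well. ORR is not affected by the 4.9 rule as written, and in the first situation 4.9 does not move the on-treatment window. This is a modest defect, worth correcting because the correction is simple.

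**What to change.** 1. In SAP 4.9, state that 4.9.7 governs the last date of study drug. Keep the existing sentence for other required end dates, such as an earlier dose record with no end date; deleting it would leave those without a rule.
2. In SAP 4.9.7, impute a missing or partial last-dose date to the earliest of analysis cut-off, death, consent withdrawal and EOT date, kept within any recorded month and year and not before the first dose. A recorded date after the cut-off stays capped at the cut-off, as 4.9 now provides.
3. Add consent withdrawal to Scenario 1, so that a patient who has withdrawn is not classed as ongoing.
4. Use that single date for duration of exposure, dose intensity and the on-treatment window.

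The cost is SAP wording and the matching program specification. No new data are needed.

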4.9.1 AE date imputation

Date imputation is the creation of a new, complete date from a partial one according to an agreed and acceptable algorithm. Missing date for AE will be handled according to rules specified below. A partial date is simply an incomplete date, e.g., DDOCT2001: the days are missing from this DDMMYYYY date.

Partial AE start dates, if left partial, would ultimately mean the following

It would not be possible to place the AE in time.

Therefore the treatment/dosage at the time of the event would be unknown.

Therefore the event could not be reported/summarized appropriately – if at all.

Therefore it is important to perform date imputation to ensure that as many data events are represented as correctly as possible. Of course partial and/or missing dates should also be caught as edit checks and passed back to the investigator for resolution.

There will be no attempt to impute the following:

- Missing AE start dates
- AE start dates missing the year
- Partial/missing AE end dates

The following [Table 4-4](#) explains the abbreviations used.

Table 4-4 AE/treatment date abbreviations

	Day	Month	Year
Partial Adverse Event Start Date	<not used>	AEM	AEY
Treatment Start Date (TRTSTD)	<not used>	TRTM	TRTY

The following matrix [Table 4-5](#) describes the possible combinations and their associated imputations. In the boxes the upper text indicates the imputation and the lower text the relationship of the AE start date to the treatment start date (TRTSTD).

Table 4-5 AE partial date imputation algorithm

	AEM MISSING	AEM < TRTM	AEM = TRTM	AEM > TRTM
AEY MISSING	NC Uncertain	NC Uncertain	NC Uncertain	NC Uncertain
AEY < TRTY	(D) Before TRTSTD	(C) Before TRTSTD	(C) Before TRTSTD	(C) Before TRTSTD
AEY = TRTY	(B) Uncertain	(C) Before TRTSTD	(B) Uncertain	(A) After TRTSTD
AEY > TRTY	(E) After TRTSTD	(A) After TRTSTD	(A) After TRTSTD	(A) After TRTSTD

The following [Table 4-6](#) is the legend to the above table.

Table 4-6 AE/treatment date relationship and imputation legend

Relationship	
Before TRTSTD	Indicates AE start date prior to Treatment start date
After TRTSTD	Indicates AE start date after Treatment start date
Uncertain	Insufficient to determine the relationship of AE start date to Treatment start date
Imputation calculation	
NC / Blank	No convention/imputation
(A)	01MONYYYY
(B)	TRTSTD+1
(C)	15MONYYYY
(D)	01JULYYYY
(E)	01JANYYYY

The following Table 4-7 gives a few examples.

Table 4-7 AE imputation example scenarios

Partial AE start date	Treatment start date	Relationship	Imputation calculation	Imputed date
12mmmyyy	20OCT2001	Uncertain	NC	<blank>
ddmmm2000	20OCT2001	Before	(D)	01JUL2000
ddmmm2002	20OCT2001	After	(E)	01JAN2002
ddmmm2001	20OCT2001	Uncertain	(B)	21OCT2001
ddSEP2001	20OCT2001	Before	(C)	15SEP2001
ddOCT2001	20OCT2001	Uncertain	(B)	21OCT2001
ddNOV2001	20OCT2001	After	(A)	01NOV2001

4.9.2 Incomplete dates of initial diagnosis, first recurrence/progression and most recent relapse/progression

Missing day is defaulted to the 15th of the month and missing month and day is defaulted to 01-Jan.

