All safety data, regardless of observation period, will be listed and assessments collected in the pre-treatment and post-treatment period will be flagged in the listings.

Adverse events

Adverse events (AEs) will be coded using the latest version of MedDRA available prior to clinical database lock and will be graded using Common Terminology Criteria for Adverse Events (CTCAE) version 4.03. If CTCAE grading does not exist for an AE, grades 1, 2, 3, or 4 corresponding to the severity of mild, moderate, severe, and life-threatening, respectively, will be used. CTCAE grade 5 (death) will not be used in this study; rather, this information will be collected on the [Death] eCRF page.

As described previously, AE summary tables will include only AEs observed during the on-treatment period (i.e., treatment-emergent AEs). All AE summaries will be tabulated (frequency counts and percentages) by primary system organ class and/or preferred term, and severity grades, except where otherwise noted. A patient with multiple CTC grades for an AE will be summarized under the maximum CTC grade recorded for the event.

The following AE summary tables will be produced:

- AEs, regardless of study drug relationship
- AEs, suspected to be study drug related
- Deaths (on-treatment deaths, all deaths during the study)
- Serious AEs, regardless of study drug relationship
- Serious AEs, suspected to be study drug related
- AEs leading to study drug discontinuation, regardless of study drug relationship
- AEs requiring dose adjustment, regardless of study drug relationship
- AEs requiring dose interruption, regardless of study drug relationship
- AEs requiring dose adjustment or interruption, regardless of study drug relationship
- AEs requiring additional therapy, regardless of study drug relationship

All AEs will be listed along with any other information (e.g., start/end dates, duration, severity, causality, action taken and outcome) as appropriate. Additional listings will be produced separately for deaths, serious AEs, AEs leading to study drug discontinuation, AEs requiring dose adjustment, AEs requiring dose interruption, AEs requiring dose adjustment or interruption, and AEs requiring significant additional therapy.

Adverse events of special interest

Adverse events of special interest (AESIs) are defined as AEs within the following categories/groupings of preferred terms:

- Hepatic toxicity
- Interstitial lung disease/pneumonitis
- QTc prolongation

- Hyperglycemia

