4.9.3 Incomplete date for anti-neoplastic therapies

Prior therapies

Start date:

The same rule which is applied to the imputation of AE/concomitant medication start date will be used with the exception that for scenario (B) will be replaced to be 'start date of study drug -1'.

End date:

Imputed date = min (start date of study drug, last day of the month), if day is missing;
Imputed date = min (start date of study drug, 31DEC), if month and day are missing.

If the end date is not missing and the imputed start date is after the end date, use the end date as the imputed start date.

If both the start date and the end date are imputed and if the imputed start date is after the imputed end date, use the imputed end date as the imputation for the start date.

Post therapies

Start date:

Imputed date = max (last date of study drug + 1, first day of the month), if day is missing;

Imputed date = max (last date of study drug + 1, 01JAN), if day and month are missing.

End date:

No imputation.

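### Rule (B) for partial AE start dates ignores the AE's own end date, so an event known to have ended before first dose can be counted as treatment-emergent

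*SAP*

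**What the plan says.** SAP 4.9.1 (Tables 4-5 and 4-6) imputes a partial AE start date from three things: the AE month, the AE year and the treatment start date. Two cells with a known year are marked Uncertain: same year with the month missing, and same year with the same month. The legend explains the label as "Insufficient to determine the relationship of AE start date to Treatment start date". Both cells use rule (B), first dose plus one day. Table 4-7 shows the result: "ddOCT2001 20OCT2001 Uncertain (B) 21OCT2001".

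End dates appear in 4.9.1 only in the list of items that will not be imputed: "Partial/missing AE end dates". The section also relies on data cleaning: "Of course partial and/or missing dates should also be caught as edit checks and passed back to the investigator for resolution".

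SAP 2.8.2 then defines the reporting window, "On-treatment period: from day of first dose of study drug to 30 days after last dose of study drug", and states that "AE summary tables will include only AEs observed during the on-treatment period (i.e., treatment-emergent AEs").

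SAP 4.9.3 borrows the AE start-date matrix for prior antineoplastic therapies, changes rule (B) to the day before first dose, and adds a check that begins "If the end date is not missing and the imputed start date is after the end date". In that case the end date becomes the imputed start. Section 4.9.1 has no such check.

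**The concern.** Protocol 8.1.1 has AEs recorded from informed consent, and Protocol 4.1.1 allows eligibility assessment up to 28 days before first dose. An AE can therefore begin and resolve during screening and be in the database. If its end date is complete and precedes first dose, its timing is settled however little is known about its start. Rule (B) still treats it as uncertain and moves it to the day after first dose.

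The stake is the separation of pre-treatment from on-treatment events on which all AE summaries depend. A screening event would enter the treatment-emergent tables, the special-interest tables if its term qualifies, and the public disclosure tables. In a study of about 20 patients a single misplaced event can be visible in the reported percentages.

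**Working it through.** **Inputs**

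- Rule (B) and the cells that use it: SAP 4.9.1, Tables 4-5 and 4-6.
- Worked examples: SAP Table 4-7, first dose 20OCT2001.
- On-treatment period starts on the day of first dose: SAP 2.8.2.
- AEs recorded from consent: Protocol 8.1.1. Screening of up to 28 days: Protocol 4.1.1.
- Planned size of about 20 patients: SAP 1.1.
- Disclosure threshold for non-serious AEs, above 5%: SAP 2.8.2.
- AE end dates used below are assumed for illustration.

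**Step 1: reproduce the plan's figures.** Coding the matrix and running the seven rows of Table 4-7 gives all seven stated results, including 21OCT2001 for ddOCT2001.

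**Step 2: add an end date.** First dose is 20OCT2001 and the AE start is ddOCT2001. The capped start is the earlier of the imputed start and the end date.

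| AE end date | Start under (B) | Period under (B) | Capped start | Period with cap |
|---|---|---|---|---|
| 10OCT2001 | 21OCT2001 | on-treatment | 10OCT2001 | pre-treatment |
| 12OCT2001 | 21OCT2001 | on-treatment | 12OCT2001 | pre-treatment |
| 19OCT2001 | 21OCT2001 | on-treatment | 19OCT2001 | pre-treatment |
| 20OCT2001 | 21OCT2001 | on-treatment | 20OCT2001 | on-treatment |
| 25OCT2001 | 21OCT2001 | on-treatment | 21OCT2001 | on-treatment |

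For the 12OCT2001 row, 21 − 12 = 9 days: the start is placed nine days after the event ended. The last two rows show that the cap leaves the on-treatment default in place when the end date does not precede first dose.

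**Step 3: find which rules misclassify.** Take every first-dose date in one assumed calendar year (2016, 366 days), and every AE that starts within the 28 days before first dose and ends before first dose. Each first-dose date gives 0 + 1 + … + 28 = 406 start/end pairs, so there are 366 × 406 = 148,596 pairs.

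| What is missing | Rule reached | Pairs | Moved on-treatment | Start after own end |
|---|---|---|---|---|
| Day | (B) | 56,028 | 56,028 | 56,028 |
| Day | (C) | 92,568 | 0 | 3,913 |
| Day and month | (B) | 140,882 | 140,882 | 140,882 |
| Day and month | (D) | 7,714 | 0 | 0 |

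Every resolved screening AE that reaches rule (B) is moved into the on-treatment period; none that reaches (C) or (D) is. Rule (C) can put a start after the end date, but the event stays pre-treatment. These counts show how the rule behaves on possible dates. They are not estimates of how often it will happen.

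**Step 4: size.** One patient in 20 is 1/20 = 5 percentage points on a preferred term, if that patient has no true on-treatment event of the term. If the patient does, the change is 0. For the disclosure table, 1/20 = 5% does not exceed the threshold and 2/20 = 10% does, so one misplaced patient can bring a non-serious term into that table.

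**The case against.** The strongest reply has four parts.

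*Treating uncertain starts as on-treatment is the conservative choice.* That is right for truly uncertain timing, and any error over-counts toxicity rather than hiding it. It does not cover an AE whose complete end date precedes first dose, because its timing is known.

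*Data cleaning will catch it.* SAP 4.9.1 calls for edit checks and queries, Protocol 8.1.1 asks for start and end dates for each AE, and Protocol 9.3 and 9.4 add automatic validation and verification before lock. These controls make the case rare. They do not replace a correct rule, since imputation acts on dates that are still partial after query.

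*Nothing says that the imputed start overrides a known end date.* The SAP speaks of AEs observed on treatment, and Protocol 10.5.3.2 of AEs new or worsening from baseline; a resolved screening AE fits neither. But 4.9.1 gives placing the event in time, so that it can be summarised, as the purpose of imputation. A programmer following it would classify by the imputed start.

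*The effect is easily overstated.* This stands. A reader might infer that all partial AE start dates go to first dose plus one day; only the two rule (B) cells do. A reader might infer that each case always adds 5 points; the tables count patients, and for common terms the patient may have a true on-treatment event as well (diarrhea 86.7%, nausea 82.7% in Protocol Table 1-1). A negative AE duration is also tempting to claim, but SAP 2.8.2 lists duration without saying that it is computed from imputed dates. An effect on the SAE tables is possible but least likely, because SAEs from consent onward are reported within 24 hours (Protocol 8.2.2).

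**Conclusion.** The gap is real and narrow. Under rule (B), an AE with a start date still partial after query and a complete end date before first dose is dated after its own end and placed in the treatment-emergent period. This is a stated rule giving a wrong result, not merely a missing detail, and the SAP already has the remedy in its next imputation rule but one.

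The size is between 0 and 5 percentage points per affected patient for a preferred term, assuming 20 treated patients and classification by imputed start date. The documents give no frequency; the conditions are restrictive and the case is probably rare. Only safety outputs are affected. ORR and the other efficacy endpoints do not depend on AE dates being imputed this way. The documents do not support reading this as a general distortion of the safety profile. Severity is low.

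**What to change.** Add one sentence to SAP 4.9.1, after Table 4-6, to this effect: *When an AE has a complete end date that is earlier than its imputed start date, the imputed start date is replaced by that end date.*

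AEs with a complete end date before first dose then fall in the pre-treatment period and are listed and flagged there. All other uncertain cases keep the on-treatment default, including an AE that ended on the day of first dose. The same sentence also repairs the start-after-end dates that rule (C) can produce.

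The cap should be limited to complete end dates. A start cannot be set to an incomplete date, and 4.9.1 does not impute partial AE end dates.

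The cost is one sentence in the SAP and one line of programming. No data collection, sample size or efficacy analysis changes.
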